5.2. Subject Distribution and Trial Completion Status

Summarise screening, enrolment, and completion numbers per centre, listing dropout cases. Provide detailed tables comparing dataset sizes across groups, case distribution per centre, overall dropout rates, reasons for screening failure, and reasons for non-completion.

5.3. Demographic data and baseline analysis

Describe patient demographics (age, gender, etc.), relevant medical history, and treatment history. Compare characteristics such as age and gender between groups to assess comparability. Demographic analysis is based on the FAS analysis set.

5.4. Efficacy Analysis

5.4.1. Primary Efficacy Endpoints

Primary efficacy evaluation is based on the Full Analysis Set (FAS) and the Per-Protocol Set (PPS).

This trial employs a multicentre, randomised, parallel-group, non-inferiority design. The primary efficacy endpoint is device procedural success rate (by lesion level), with the following hypothesis testing:

$$H_0 : p_T - p_C \leq -\Delta$$

$$H_1 : p_T - p_C > -\Delta$$

In the formula, $p_{(T)}$ denotes the device usage success rate for the experimental group, p_C represents the device usage success rate for the control group, and $-\Delta$ signifies the non-inferiority margin, set at -10%.

At $\alpha=0.025$ (one-sided test) and $\beta=0.2$, the device procedural success rate (by lesion level) of the experimental group is compared with that of the control group. The difference in device procedural success rates (by lesion level) between the two groups is calculated, along with the 95% confidence interval for this difference. Based on the lower limit of the confidence interval, a judgement is made as to whether the non-inferiority criterion has been met. If the lower limit of the 95% confidence interval is not less than -10%, the conclusion of non-inferiority is established. Should centre effects require consideration, the CMH chi-square test shall be employed.

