## **5.2 Subject Enrollment**

### **5.2.1 Inclusion Criteria**

- (1) Patients are at least 18 to 75 years of age, male or not pregnant female;
- (2) Patients with asymptomatic ischemic evidence, stable or unstable angina pectoris or old myocardial infarction;
- (3) In situ or restenotic lesion(s) in coronary arteries, including in-stent restenosis (ISR);
- (4) Target lesion(s) must have a diameter of 2.0 mm ~ 3.5 mm and a length of  $\leq 30$  mm;
- (5) Target lesion(s) must have a percent diameter stenosis of  $\geq 70\%$  or  $\geq 50\%$  with evidence of ischemia;
- (6) Patients have a planned intervention at no more than two lesions, in different target vessels;
- (7) Investigators believe that target lesion atherosclerotic plaques require the scoring balloon treatment, in which the balloon can be passed through by pre-dilation.
- (8) Able to understand the purpose of the trial, voluntarily participate and sign the ICF.

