### 6.1.2 Allocation of Sample Size

The inclusion/exclusion criteria for the selected subjects are strictly restricted in this trial protocol, and all selected 136 subjects are diagnosed with coronary artery stenosis (including in situ or restenotic lesions). The subjects screened are randomized at 1:1 to receive the investigational medical device or the control device for treatment, and the device success rate is set as the primary endpoint.

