### (3) Primary efficacy endpoint

The Primary efficacy endpoint of this study is the device success rate (lesion level), and the hypothesis test is as follows:

Null hypothesis:  $P_T - P_C \leq -10\%$

Alternative hypothesis:  $P_T - P_C > -10\%$

Under  $\alpha=0.025$  (one-sided test) and  $\beta=0.2$ , the device success rate (lesion level) is compared between the test group and control group, and the difference between the two groups and the 95%CI of such difference are calculated to determine whether the non-inferiority margin is met based on the lower limit of CI. Non-inferiority is established if the lower limit of 95%CI is not lower than -10%. If

central effect is to be considered, CMH's chi-square test is used.

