1.5. Sample size

Based on literature review, clinical experience, and results from studies evaluating scoring balloon catheters for coronary artery disease, it is hypothesised that the study group's Sino scoring balloon dilation catheter will demonstrate comparable efficacy to the control group's Goodman coronary NSE balloon catheter, with an anticipated device success rate of 96%. Considering factors such as operator skill variation, lesion complexity, and subject comorbidities and disease severity, the sponsor, clinical experts, investigators, and statisticians jointly determined a non-inferiority margin Δ of -10%, a one-sided test α of 0.025, and a test power (1- β) of 0.8. PASS software calculations yielded a total sample size of 122 subjects, with 61 subjects in each group. Accounting for a 10% dropout rate, the trial requires 136 subjects, distributed as 68 in each group. The sample size calculation formula is as follows:

$$n_T = n_C = \frac{\left(Z_{1-\frac{\alpha}{2}} + Z_{1-\beta}\right)^2 [P_C(1 - P_C) + P_T(1 - P_T)]}{(|D| - \Delta)^2}$$

Where n_T and n_C denote the sample sizes for the treatment and control groups respectively, $Z_{1-\frac{\alpha}{2}}$ and $Z_{1-\beta}$ represent the quantiles of the standard normal distribution, P_T and P_C denote the expected event rates for the treatment and control groups respectively, $|D| = |P_T - P_C|$ denotes the absolute difference in expected rates between the two groups, and Δ denotes the non-inferiority margin, taken as a negative value.

This trial will be conducted concurrently across multiple clinical trial sites. In principle, enrolment numbers will be distributed as evenly as possible among centres to ensure adequate representativeness. However, considering feasibility and enrolment progress, adjustments to enrolment quotas for participating sites will be made based on actual circumstances, striving to maintain balanced enrolment scales across centres. The final enrolment size for any single centre shall not exceed 50% of the total number of cases.

2. Evaluation Criteria

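### The deciding confidence interval compares lesions between arms randomised by subject, with no allowance for two target lesions in one subject, so it is too narrow if paired outcomes are positively correlated

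*SAP*

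**What the plan says.** **Unit of randomisation.** Protocol 6.1.2: "The subjects screened are randomized at 1:1". SAP 1.3 likewise allocates subjects, not lesions.

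**Unit of analysis.** Protocol 6.4.2 (3) says that "the device success rate (lesion level) is compared between the test group and control group", and SAP 5.4.1 repeats this: "the device procedural success rate (by lesion level) of the experimental group is compared with that of the control group". SAP section 4 also imputes per lesion, counting a lesion that cannot be assessed as a device failure. Non-inferiority rests on the lower limit of the 95% CI for the lesion-level difference against -10%.

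**Lesions per subject.** Protocol 5.2.1: "Patients have a planned intervention at no more than two lesions, in different target vessels". The secondary endpoint asks for at least one target lesion with acceptable residual stenosis, and SAP Table 11 has a row for subjects with two target lesions. The plan therefore provides for such subjects.

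**Methods named.** SAP 5.1 gives chi-square or exact tests for categorical data. SAP 5.4.1 adds CMH if centre effects need considering. Note 1 to SAP Table 19 leaves the CI method as the placeholder XX. Neither document mentions clustering, a robust variance, a mixed model or GEE, or a rule of one lesion per subject.

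**Sample size.** SAP 1.5 counts subjects: "PASS software calculations yielded a total sample size of 122 subjects, with 61 subjects in each group".

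**The concern.** Two lesions treated in one subject share the operator, the session, the assigned device and the subject's own risk. Protocol 6.1.1 itself lists operator level and subject comorbidity and severity among the factors weighed in setting the margin. Positive correlation between paired outcomes is therefore plausible on the plan's own reasoning.

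Chi-square, exact and CMH-by-centre methods, and the usual two-proportion interval, treat each record as independent. Applied to correlated pairs, they count more information than the data hold. The standard error is then too small, the lower limit sits too high, and a device truly at the margin passes more often than it should. This is the trial's only confirmatory test, and the error runs in the sponsor's favour.

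**Working it through.** **Inputs from the documents:** 96% success expected in both arms; margin 10 points; "a one-sided test α of 0.025, and a test power (1- β) of 0.8"; 10% dropout; at most two planned lesions per subject.

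**Assumed, because the documents do not give them:** f, the share of subjects with two target lesions, and ICC, the correlation between the two outcomes in one subject.

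**1. The plan's own figure.** n = (1.96 + 0.842)² × (0.96×0.04 + 0.96×0.04) / 0.10² = 7.85 × 0.0768 / 0.01 = 60.3, so 61 per group. 61/0.9 = 67.8, so 68 per group and 136 in all. The stated size reproduces. The formula takes one independent observation per subject.

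**2. Design effect.** With n subjects per arm, Σm = n(1+f) lesions and Σm² = n(1+3f). Then DE = 1 + ICC × (Σm²/Σm − 1) = 1 + ICC × 2f/(1+f). For example, f=20% and ICC 0.3 give 1 + 0.3×0.4/1.2 = 1.10.

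**3. Normal approximation, 68 subjects per arm, 96% in both arms.** Unadjusted half-width = 1.96 × √(0.0768/[68(1+f)]). The clustered half-width multiplies this by √DE. One-sided error of the unadjusted rule = 1 − Φ(1.96/√DE).

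| f | ICC | DE | Half-width, unadjusted → clustered (points) | One-sided error |
|---|---|---|---|---|
| 10% | 0.3 | 1.05 | 6.28 → 6.45 | 2.8% |
| 20% | 0.3 | 1.10 | 6.01 → 6.31 | 3.1% |
| 20% | 0.5 | 1.17 | 6.01 → 6.49 | 3.5% |
| 50% | 0.5 | 1.33 | 5.38 → 6.21 | 4.5% |

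With f=0 or ICC=0 nothing changes.

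**4. Simulated error at the margin.** True rates 86% and 96%, 68 subjects per arm, 100,000 to 400,000 trials per setting. Ranges span separate runs.

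| f | ICC | Unadjusted Newcombe | Unadjusted Wald | Newcombe on Rao-Scott effective counts |
|---|---|---|---|---|
| 0 | – | 2.1–2.2% | 4.2% | unchanged |
| 10% | 0.1–0.3 | about 2.3–2.5%* | 3.9–4.5% | 2.2–2.4% |
| 20% | 0 | 2.2–2.4% | 3.6–3.8% | 2.1–2.2% |
| 20% | 0.3 | 2.8–3.0% | 4.4–4.5% | 2.4% |
| 20% | 0.5 | 3.2% | 4.9–5.0% | 2.5–2.6% |
| 50% | 0.5 | 4.2–4.5% | 5.8–5.9% | 2.6–2.8% |

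*When the number of two-lesion subjects varies by chance. With it fixed at seven per arm, the figure is 2.6–2.9%. Differences of this order partly reflect the discreteness of the counts: with that number fixed, independence alone gives about 2.5%.

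**5. Simulated power, both arms 96%, Newcombe, unadjusted → Rao-Scott.** At f=20%: about 79% → 74–75% (ICC 0.3) and 78% → 71–72% (ICC 0.5). At f=50%, ICC 0.5: 86% → 75–76%. If lesions are independent the loss is about 1 point.

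**The case against.** **The harm is conditional.** It needs subjects with two target lesions and positive correlation, and the documents quantify neither. Protocol 5.5.3 allows the second treated lesion to be a non-target lesion, so many two-lesion patients may contribute one analysed lesion. Table 11 shows that two target lesions are possible, not how often they occur. The f=50% case has no support in the documents. This stands, and it is why the size is given only as a range.

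**Correlation may be low.** The two lesions must lie in different vessels, and crossing and residual stenosis depend partly on the individual lesion. This also stands. At f=20%, ICC 0.1, the unadjusted Newcombe interval stays at about 2.4%.

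**Independence is inferred.** The SAP never says that lesions are independent, and the CI method is blank. That is true, but every named method has this effect and nothing in either document tells the analyst to do otherwise.

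**Inferences to avoid.** A reader might take the Wald figures of 4.4–5.9% as the cost of ignoring clustering. Most of that excess is the Wald interval's own small-sample error (about 3.7–4.2% without clustering), and the SAP does not name Wald. A reader might also infer that clustering leaves the trial short of subjects. By the normal approximation with a clustered variance, 61 subjects per arm keep at least 80% power for ICC up to 0.5, because second lesions add information. Power drops to about 76–78% only near ICC = 1. The Newcombe interval has only about 70% power at 68 per arm even with one lesion per subject, so a shortfall against 80% is not all due to clustering.

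**Conclusion.** The mismatch between the unit of randomisation and the unit of analysis is real, and the plan as written does not handle it. Given any two-target-lesion subjects with positively correlated outcomes, the deciding interval is too narrow and favours non-inferiority.

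The size is uncertain. It is negligible at f=10% with low ICC, about 0.3–0.7 points above the nominal 2.5% at f=20% with ICC 0.3–0.5, and nearly 2 points above it at f=50%, ICC 0.5 (Newcombe, 68 subjects per arm). A reader might infer that the error rate certainly exceeds 2.5%. The documents do not support that, because f and ICC are unknown and a Newcombe interval starts slightly below nominal in most settings.

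The case for acting now does not depend on the exact size. The CI method is still blank, the choice could decide a close result, and Protocol 6.4.7 requires the SAP to be final before database lock.

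**What to change.** In SAP 5.4.1 and Table 19 Note 1, keep the lesion-level rate difference and the -10% margin. Replace the placeholder with a named CI that takes the subject as the cluster and performs well near 96%. One option that held error at about 2.1–2.8% in the settings above is a Newcombe or score-type interval on effective counts: divide each arm's lesion counts by a Rao-Scott design effect computed from subject clusters, floored at 1. GEE, a cluster-robust variance or a subject-level bootstrap address the same problem, but their behaviour near 96% should be checked first. An unadjusted Wald interval should not be used in any case.

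Add one supportive subject-level analysis in which a subject succeeds only if every target lesion succeeds.

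**Cost:** SAP wording and a few lines of code, with no new data or patients. The interval widens. Compared with the unadjusted Newcombe interval, power falls by roughly 4–8 points at f=20%, ICC 0.3–0.5, by 10–11 points at f=50%, ICC 0.5, and by about 1 point if lesions are independent. Under correlation, the power given up came from counting correlated lesions as independent. With about three failures expected per arm at 96%, the estimated design effect will be noisy, which is a further reason to fix the method before the outcome data are seen.

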#### **5. Study Design**

##### **5.1 Overall Design and Its Determination Basis**

This clinical trial is a prospective, multicenter, randomized, parallel controlled, non-inferiority design.

Multicenter clinical trial: refers to the clinical study conducted in two (inclusive) or more medical device clinical trial institutions under the same clinical trial protocol.

Parallel controlled design: Based on the Guidance for the Design of Medical Device Clinical Trials, the controlled clinical trial is conducted using the marketed devices with recognized efficacy/safety. The Coronary Scoring Balloon Catheter is a class III medical device, and there are few similar products on the market. In order to evaluate the effectiveness and safety of Coronary Scoring Balloon Catheter, the NSE Coronary Dilatation Catheter (NMPA (I) 20163035067), which is similar in structure and operating principle, relatively widely used in clinical practice and has positive efficacy in China and abroad, is

selected as the control device after investigation.

**Randomization:** Randomization is the basic principle to be followed by parallel controlled clinical trials. Each subject in a clinical trial has the same opportunity (the ratio of cases in test group to control group is 1:1) to be assigned to test group or control group, without affection of subjective wishes of the investigator and/or subject, to ensure the subjects in test group and control group comparable in various known and unknown baseline variables that may affect the trial result.

**Blinding:** Due to the different inherent characteristics (appearance, marking, etc.) of the investigational medical device and the control device, the subjects and investigators cannot be blinded in the trial, so an open-label design is adopted.

**Non-inferiority test:** The non-inferiority test is selected to confirm the efficacy/safety of the investigational medical device, which if lower than that of the control device but the difference between them is less than the pre-set non-inferiority margin, the difference is clinically acceptable.

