### **6.4.7 Procedures for Reporting Deviation from Original Statistical Plan**

The statistical analysis plan needs to be confirmed by the sponsor and the PIs, and finalized before database locking. Prior to finalization, the initial analysis plan should be modified according to the actual conditions in the trial process. In principle, the main analysis principles, methods and analysis sets should not be modified, and all the modifications will be recorded.

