6.6. Efficacy Endpoints (FAS、PPS)

6.6.1. Primary Efficacy Endpoints

Table 18 Device procedural success (18)

Project	Indicator	FAS	Control Group	PPS	Control Group
		Experimental group		Experimental Group	
Device	Success n(%)				

Project	Indicator	FAS		PPS	
		Experimental group	Control Group	Experimental Group	Control Group
procedural Rate	Failure n(%)				
	Total (Missing)				
	Single-group				
	success rate 95% CI				
	Statistic (CMH)				
	P-value				

Note 1: Device procedural success (by lesion level) requires simultaneous fulfilment of the following conditions: a. Successful completion of the entire balloon dilatation procedure, including delivery, lesion crossing, inflation, deflation, retraction, and withdrawal; b. Immediate post-PCI target lesion residual stenosis $\leq 30\%$ (for in-stent restenosis and drug-coated balloon restenosis lesions, post-procedural residual stenosis $< 50\%$). a. Partial analysis presented in Table 20: Device Evaluation; b. Partial analysis presented in Table 21: Immediate Post-PCI Target Lesion Residual Stenosis.

Note 2: For patients in the FAS cohort where the primary efficacy endpoint was not observable, worst observation carried forward was applied; subjects where assessment was inconclusive were counted as failing device use success.

Table 19 Device Success Rate (Lesion Level) Hypothesis Test

Population	Parameter	Experimental group n(%)	Control Group n(%)	Difference in Rates		P	Non-inferiority margin
				Between Groups	Difference in rates between groups Two-sided 95% CI		
FAS	Experimental group - Control group						-10%
PPS	Experimental group - Control group						-10%

Note 1: Rate difference = Experimental group - Control group. The non-inferiority margin is -10%. The 95% confidence interval for the rate difference was calculated using the XX method.

Note 2: The lower limit of the 95% confidence interval for the intergroup success rate difference exceeds -10%, establishing the non-inferiority hypothesis.

Table 20 Device Evaluation (Lesion Level)

Item	Indicator	FAS		PPS	
		Experimental Group	Control Group	Experimental Group	Control group
Device usage success	Yes n(%)				
	No n(%)				

Item	Indicator	FAS		PPS	
		Experimental Group	Control Group	Experimental Group	Control group
Balloon successfully advanced to lesion	Total (Missing)				
	Statistic				
	P-value				
	Yes n (%)				
	No n(%)				
	Total (Missing)				
Balloon successful passage through lesion	Statistic				
	P-value				
	Yes n (%)				
	No n(%)				

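### The only method named for centre effects, a CMH chi-square, cannot address the -10% margin, and the confidence interval that decides non-inferiority has no named method

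*SAP*

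**What the plan says.** SAP 5.4.1 and Protocol 6.4.2(3) state the null hypothesis as a difference of -10% or worse, and establish non-inferiority from the lower limit of the 95% CI for the rate difference. Protocol 6.4.5 makes that limit the only pass/fail criterion.

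For centre effects, the SAP adds "Should centre effects require consideration, the CMH chi-square test shall be employed", and the Protocol says that if "central effect is to be considered, CMH's chi-square test is used". Neither says when centre effects count as needing consideration, and neither gives a centre-adjusted difference or interval. SAP Table 22 lists success by centre without combining the centres.

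SAP Table 18 (success counts) has a row for a CMH statistic and a P-value. SAP Table 19 is the hypothesis test, with the difference, its CI, a P-value and the margin. Its first note reads: "The 95% confidence interval for the rate difference was calculated using the XX method". The methods text of SAP 5.4.1 and Protocol 6.4.2(3) names no CI method either.

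On changes to the plan, Protocol 6.4.7 says: "Prior to finalization, the initial analysis plan should be modified according to the actual conditions in the trial process". It also requires finalization before database lock, says the main methods should in principle stay unchanged, and requires every modification to be recorded.

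**The concern.** There are two gaps in the primary analysis.

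First, the standard CMH chi-square has as its null hypothesis no association within centres, that is, a difference of zero. The trial's null is a difference of -10% or worse. A non-significant CMH result does not show that the difference lies above -10%, and CMH yields no interval to set against the margin. If centres differ, the plan has no way to show whether the non-inferiority conclusion survives adjustment.

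Second, the pass/fail rule depends on a confidence limit whose formula is not given. At success rates near 96% with about 68 lesions per arm, two or three failures per arm are expected, and the common formulas disagree by more than a percentage point. The plan therefore does not determine the verdict for every possible result. The trial is open-label, so the formula should be fixed in writing before lock.

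**Working it through.** **Inputs.** From SAP 1.5: "with an anticipated device success rate of 96"% in both arms; "non-inferiority margin Δ of -10%, a one-sided test α of 0.025, and a test power (1- β) of 0.8"; 61 evaluable and 68 enrolled per arm. From Protocol 5.1: 1:1 allocation. Assumption for all results at 61 or 68 per arm: one lesion per subject. The primary endpoint is at lesion level and up to two lesions are allowed, but the expected number is not stated.

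**1. The plan's sample size.** n = 7.85 × (0.96×0.04 + 0.96×0.04) / 0.10² = 7.85 × 0.0768 / 0.01 = 60.3, so 61 per arm. 61/0.90 = 67.8, so 68. This matches "PASS software calculations yielded a total sample size of 122 subjects, with 61 subjects in each group". The formula is the unpooled normal approximation, so the stated 80% power corresponds to a Wald interval.

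**2. What CMH can show.** Exact binomial enumeration with 68 per arm and true rates of 86% and 96%: CMH gives p>0.05 in 44% of trials with one stratum. Simulation with 3, 5 or 8 equal centres (assumed, no true centre differences) gives 45-46%. With 96% in both arms, CMH is significant in favour of the test device in only 2.3% of trials.

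Example, 63/68 against 66/68, one stratum: expected successes 64.5; variance = 68×68×129×7/(136²×135) = 1.672; chi-square = 1.5²/1.672 = 1.35, p = 0.25. The lower limits are -11.8% (Wald), -13.4% (Newcombe) and -13.6% (Miettinen-Nurminen). Non-inferiority fails under all three.

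**3. Does the CI method matter?** Take 64/68 (94.12%) against 66/68 (97.06%), difference -2.94%.
- Wald: SE = √(0.9412×0.0588/68 + 0.9706×0.0294/68) = 0.03513; lower limit = -0.0294 - 1.96×0.03513 = -9.8%. Pass.
- Newcombe: Wilson lower limit for 64/68 is 0.8583, upper limit for 66/68 is 0.9919; lower limit = -0.0294 - √[(0.9412-0.8583)² + (0.9919-0.9706)²] = -0.0294 - 0.0856 = -11.5%. Fail.
- Miettinen-Nurminen: score statistic at -10% is 1.65, below 1.96; lower limit -11.7%. Fail.

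**4. Operating characteristics** of the rule that the lower 95% limit exceeds -10%, by exact enumeration:

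| Method | Error at 86%/96%, 68 per arm | Power at 96%/96%, 68 per arm | Power at 96%/96%, 61 per arm |
|---|---|---|---|
| Wald | 4.2% | 85.3% | 81.9% |
| Agresti-Caffo | 3.0% | 78.9% | 74.2% |
| Newcombe | 2.2% | 69.8% | 66.3% |
| Miettinen-Nurminen | 2.2% | 69.8% | 64.6% |

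At 96%/96% and 68 per arm, Wald passes while Newcombe fails in 15.5% of trials.

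**5. More lesions.** With 136 independent lesions per arm, an upper bound, power is 96-98% for every method. Wald's error is then 3.3%.

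**6. A centre-adjusted alternative.** A Mantel-Haenszel risk difference with the Sato variance (68 per arm, 3 to 8 equal centres) has power of about 85% but error of 4.1-4.3%. It tests the margin, but it shares Wald's excess error.

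**The case against.** The strongest reply is that the plan cannot reach a wrong conclusion through CMH. A reader might infer that the primary test changes to CMH once centre effects are considered, or that a non-significant CMH could count as success. The documents do not support this. The CMH sentence follows the confidence-limit rule without withdrawing it, Protocol 6.4.5 says non-inferiority is otherwise not established, and Table 19 repeats the criterion. In the 63/68 against 66/68 example the trial fails under the written rule whatever CMH shows. Nor does Table 18 call CMH the primary statistic; it is one row beside counts and single-group intervals. All of that stands, and it makes the CMH point a gap in the centre-adjusted analysis rather than a faulty decision rule.

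A reader might also take XX as a sign that the method will be chosen once results are known. It looks like an unfilled template field, as in the core-laboratory notes to Tables 12 and 24. Protocol 6.4.7 restricts changes to main methods and requires them to be recorded. No intent is shown. But that restriction cannot protect a method that was never specified.

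Finally, the size of the problem depends on one lesion per subject, and the power gap largely closes if there are many more independent lesions. That is fair, but the plan does not state a lesion count, and two lesions in one subject need not be independent.

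**Conclusion.** The concern holds in two parts. The only centre-effect method named for the primary endpoint does not address the trial's hypothesis: at the margin it is non-significant in about 44% of trials with 68 per arm, and it supplies no adjusted interval. Separately, the deciding interval has no method. For results such as 64/68 against 66/68 that omission settles the verdict, and Wald would carry a one-sided error of 4.2% where the plan states 2.5%.

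The confidence-limit rule itself is sound and remains the sole criterion. The error and power figures rest on one lesion per subject and on true rates of 96%, or 86% against 96%. The multi-centre figures also assume equal centres without true centre differences.

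**What to change.** **Deciding interval.** In SAP 5.4.1 and the Table 19 note, name before database lock a method that holds the one-sided 2.5% error. Miettinen-Nurminen stayed at or below 2.4% in every case computed (61, 68 and 136 per arm; control rates 96%, 95% and 90%). Newcombe is an acceptable alternative, although it reached 2.6% in some of these cases.

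**Centre effects.** In SAP 5.4.1 and Protocol 6.4.2(3), replace the CMH chi-square with a centre-stratified risk difference and its 95% CI, compared with -10%, as a sensitivity analysis. Use a stratified score interval rather than Mantel-Haenszel with a Wald-type variance. State in advance how small centres are pooled. Label any CMH P-value in Table 18 as descriptive.

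**Cost.** The wording is cheap, but the power consequence is not. Under 96%/96% with one lesion per subject, power falls from about 85% to about 70% at 68 per arm, and from about 82% to 65-66% at 61. The stated 80% must be restated for the chosen interval, together with the expected number of lesions per subject.
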